6.1.2 Usual care

Participants randomised to usual care alone will receive stroke aftercare in line with their local standard of care.

6.1.3 Stroke Action Falls in addition to usual care

Participants randomised to SAF and usual care will receive stroke aftercare in line with their local standard of care as well as the SAF intervention in line with section 4.3 Stroke Action Falls (SAF) visits.

6.2 FOLLOW-UP

Table 6: Data collection schedule

	0												
Timepoint (month)	(baseline)	1	2	3	4	5	6	7	8	9	10	11	12
Assessment													
Fall Diary		Х	Х	Х	Х	Х	Х	Х	х	Х	Х	Х	Х
Short FES-I	x						Х						Х
PHQ - patient	x						Х						Х
PHQ - carer	x						Х						Х
NEADL	X						Х						Х
Modified Barthel Index	x												
EQ-5D-5L	x			Х			Х			Х			Х
Health Resource use				Х			Х			х			Х
SAF sessions	X (≤2 weeks)	Х			(x)*		Х						

^{*}Triggered SAF sessions, can take place any time up to 6 month visit.

All participants and their carers will be asked to complete study questionnaires up to 12 months post-randomisation in line with Table 6: Data collection schedule.

6.2.1 Monthly Falls Reporting

Follow-up of participants will start one month after randomisation and continue for the duration of their 12-month participation. Participants will be asked to keep a record of any fall they have during their 12-month participation. Participants will be provided with Falls Diary to support recollection of the falls they have had each month. The use of the Falls Diary will be encouraged but not mandated and Falls Diaries will not be considered source data.

Page 34 of 53

FISS Protocol Final Version 1.0 date 24-Jul-2025

Each month, participants will be contacted about any falls they may have had in the previous 30 days. They will be asked up to three questions about their falls; if they have fallen; how many falls they have had and the severity of each of the falls. Monthly falls reporting will be collected electronically, via telephone or via post using paper forms (if required). If a participant has not fallen in the previous 30 days, they will need to complete the monthly falls report as no falls for that reporting period.

Falls severity will be assessed using the National Database of Nursing Quality Indicators (NDNQI) [12] scale. The scale categorises falls into five levels, however for the purpose of the study, only four will be used: none, minor, moderate and major. The fifth level, death, won't be self-reported via questionnaires.

6.2.2 3-and 9-month follow-up questionnaires

Participants will complete a questionnaire pack (online, postal or telephone) 3- and 9-months after randomisation which will include the following:

- Quality of Life (EQ-5D-5L) [16]
- Health Resource Questionnaire

6.2.3 6-and 12-month follow-up questionnaires*

Participants and their carers will complete a questionnaire pack (online, postal or telephone) 6- and 12-months after randomisation which will include the following:

- Nottingham Extended Activities of Daily Living (NEADL) [14]
- Short Falls Efficacy Scale-International (Short FES-I) [13]
- Patient Health Questionnaire (Participant PHQ) [15]
- Quality of Life (EQ-5D-5L) [16]
- Health Resource Questionnaire
- Patient Health Questionnaire (Carer PHQ)
- * Where participants are not able to complete to questionnaires themselves or have a family or friend to support questionnaire completion, additional support may be available from their local stroke service. Availability of this will depend on local service resource and may vary from service to service.

There will be the option to complete questionnaires at all timepoints online, by post or telephone (where possible). Outstanding questionnaires not received back from participants will be followed up by a member of the central research team (e.g. email, SMS, post or telephone reminders). Questionnaire data may be completed over the telephone where necessary to increase data completeness.

Participants will be asked to complete the questionnaires themselves, but where this is not possible, participants can be supported by another person (e.g., a family member or friend) to complete as appropriate.

Participants and carers will be advised that questionnaires should be completed within approximately 4 weeks of being sent (e.g. scheduled completed date +4 weeks). Questionnaires completed and returned after this time will be analysed according to the SAP.

6.2.4 Use of prompts and reminders

Participant and personal consultee (where relevant) contact details will be collected as part of the informed consent process. Strategies to minimise loss to follow-up will include online

Page 35 of 53

FISS Protocol Final Version 1.0 date 24-Jul-2025

(website) newsletters communicating study progress, and e-mails, text messages and phone calls will be sent/made to prompt completion of follow-up questionnaires. Participants may also be contacted by a member of the study team by telephone to collect primary outcome falls data.

Participants and personal consultees (where relevant) name and telephone number will be shared with Esendex, our text messaging provider and their subprocessors, and will be used to send text message reminders about the study and study questionnaires.

6.3 ADHERENCE

6.3.1 Adherence to SAF intervention delivery

Fall Leads' adherence to delivering the intervention to protocol will be monitored via the electronic Case Report Form (eCRF) where each intervention session will be recorded with information of the format and length of the session. Any reasons for non-compliance, such as a session not taking place, will be documented in the eCRF.

Adherence to SAF intervention delivery will be monitored and reported regularly to the TMG according to the current version of the monitoring plan.

6.3.2 Patient adherence to SAF action plan

SAF is a self-directed intervention to be actioned by the participant (with support from family etc. as required). A participant's ongoing adherence to the SAF intervention cannot be observed outside of SAF intervention sessions therefore adherence to the intervention will not be captured in the eCRF. A subset of participants randomised to the intervention will be interviewed to better understand their views on the action plan as part of the study process evaluation, see section 9 for more details.

6.4 PROTOCOL DEVIATIONS AND NON-COMPLIANCES

Protocol non-compliance will be monitored via central monitoring of eCRF data. Where non-compliances are detected, they will be reviewed by the TMG and recorded and escalated to the Sponsor and other committees as required.

Where the outcome of the initial assessment is a serious breach or other serious protocol violation, it will be reported immediately to the CI and further investigated following the relevant NCTU SOPs.

The CI will notify the Sponsor if a deviation or violation has an impact on participant safety or integrity of the study data. The Sponsor will advise on appropriate measures to address the occurrence which may include reporting of a serious Good Clinical Practice (GCP) breach, conduct of an internal audit of the study, and seeking counsel of the study committees and the REC.

6.5 CRITERIA FOR TERMINATING STUDY

On the recommendation of the TSC, the Sponsor (in collaboration with the TMG) may stop the study if emerging evidence of efficacy or major safety concerns arise, or if there are significant concerns regarding study conduct. There should be proof beyond reasonable doubt for overall efficacy or major safety concerns (internal or external evidence) for the TSC, DMC and TMG to recommend the study is stopped.

Page 36 of 53

FISS Protocol Final Version 1.0 date 24-Jul-2025

Stroke services may be closed to recruitment prior to the end of the study if the TMG identifies unacceptable performance related to monitoring triggers (outlined in the current version of the FISS Monitoring Plan). In the case where a participating service closure has been decided, the TMG may make this decision without consultation with the TSC. Where screening and recruitment activity has taken place, research data should not be destroyed (it should be archived according to the archiving section below).

If following the pilot phase the study is not deemed feasible to continue (using the agreed criteria) and the funding is discontinued, the study will be terminated.

7. STATISTICS AND DATA MANAGEMENT PLAN

7.1 DATA MANAGEMENT PLAN

The Data Management Plan (DMP) for this study is a standalone document and is stored/maintained centrally within NCTU systems. The current version of the DMP contains detailed information regarding data capture, queries, validation, cleaning and database lock and will be finalised prior to commencement of recruitment.

7.1.1 General

The DMP will include the agreed roles and responsibilities for the study data and user access. Additional manual and electronic reviews may also be conducted, and data queries / clarifications may arise from such reviews. Data validation is covered by the data validation document (DVD).

The study database to be used is REDCap. It is a validated secure web-based platform which allows for data tracking via date stamped audit logs. FISS participants will be identified on REDCap only by a unique participant identifier (their study/participant ID) and initials to protect from bias and ensure confidentiality.

Data will be held on secure servers. These servers are located within The University of Nottingham data centres, which are managed and monitored regularly. Security is both physical (secure limited role-based access) and electronic (behind firewalls, access via user accounts (username and password) on encrypted connections, restricted access for some users (e.g. stroke service staff) who only have access to their patient data, and by user type/role). All access and data transactions will be logged in a full audit trail.

7.1.2 Data Capture and Data Queries

All study data will be entered onto the study specific database through the secure eCRF.

Data will be collected and entered by the local research team and directly from participants who receive a secure link via a text message or email for online questionnaires. Participants who are unable or unwilling to complete online questionnaires will be offered alternatives to complete data (e.g. by post, telephone or in-person). Questionnaire data returned to the NCTU will be entered into the database by the NCTU research team. More information on who captures the data is listed in the current version of the FISS DMP.

Only staff listed on the delegation log and training log will be given access to the relevant sections of the study database e.g., stroke service 1 staff will only have access to stroke service 1 study participants while the study team including the research teams will have access to the wider database. Individual study and research team member access will vary depending on role and associated blinding status.

Page 37 of 53

FISS Protocol Final Version 1.0 date 24-Jul-2025

Data reported on each eCRF will be checked for missing data or discrepancies and will be queried. Staff delegated to complete eCRFs will be trained to adhere to relevant aspects of GCP associated with data entry.

Data queries will not be raised on participant or carer completed questionnaires.

7.1.3 Description of Data Entry Validation

Programmed validation and manual checks will be used to identify data anomalies. All programmed validation checks are documented in the data dictionary and data quality rules on the REDCap database.

Programmed validation checks will automatically flag discrepancies at the point of data entry or will be executed by data management at the point of data cleaning. Data identified as missing or having discrepancies, may require a manual data query to be raised within REDCap by the Data Management team at NCTU.

7.1.4 Data Cleaning and Database Lock

Once all data has been collected, is cleaned and signed off by the local PIs, the study database will be locked.

The database will be hard locked as per the relevant NCTU SOP using the associated checklist. All user rights will be removed, and it will be read only. Further details will be included in the current version of the study DMP.

7.1.5 Monitoring

Onsite and central monitoring will be carried out as required, following a risk assessment and as documented in the current version of the study Monitoring Plan.

7.2 STATISTICS

7.2.1 Methods

The study will be analysed and reported in accordance with CONSORT guidelines for RCTs[18] and in line with the guidance for evaluation of complex interventions[19]. A detailed Statistical Analysis Plan (SAP) will be finalised prior to database lock and treatment allocation release. The study and senior study statisticians will be blinded to treatment allocation throughout the study.

Primary analyses: The primary analyses, after 12 months follow-up of all participants, will be as randomised (intention to treat) without imputation of missing data and will use a negative binomial model including minimisation factors and incorporating exposure time to estimate the between group difference and placing due emphasis on the 95% confidence intervals. Sensitivity analyses will be performed to determine the impact of missing data and may also include further co-variates if visual inspection of baseline variables show marked imbalanced between groups.

Baseline and secondary outcomes: Baseline variables will be summarised using descriptive statistics only and presented by treatment group. Secondary outcomes will be analysed using appropriate regression models which include the minimisation factors and the baseline value of that variable where available. Associated measures of the between treatment difference such as the difference in means, will be presented alongside 95% confidence intervals. The

Page 38 of 53

FISS Protocol Final Version 1.0 date 24-Jul-2025

secondary analyses will be considered supportive to the primary and interpreted in that light, and no multiplicity adjustments will be made.

No interim analyses are planned in this study.

7.2.2 Sample size and justification

We assume that stroke survivors will have an annual falls rate somewhere between that in community dwelling stroke survivors up to 5 years post stroke in the FAST study (1.8 falls per year) and that of participants in care homes observed in the FinCH study (3.2 falls per year). Using the upper limit of the 95% confidence interval for the overdispersion parameter (FinCH study; 1.1) and assuming an annual falls rate of 2.5 falls per year per participant, 416 evaluable participants would be required to detect a relative difference of 33% in falls rates (i.e. to 1.675 falls per year) using a negative binomial model, with 90% power at the 5% significance level (2-sided) – or 208 per arm. Sample size calculations were performed using PASS 2022 (NCSS).

This difference was deemed a clinically important difference by our FISS PPI group and in the FinCH study. A survey of occupational health professionals showed that 15/27 (58%) would consider adoption of the SAF program if the falls rate was reduced from 3 to 2 falls per year (a 33% reduction), with 3/27 (11.5%) saying they would not consider adoption.

The negative binomial model takes into account exposure, but there is a risk that no robust primary outcome data are collected from some individuals. Therefore, we will inflate the sample size by 10% and aim to randomise 464 participants, or 232 per arm. This sample size also provides 90% power to detect a relative difference of 34% and 36% if the falls rate was lower than expected at 2 and 1.5 falls/year.

The primary outcome event rate is based on the best evidence currently available. However, we recognise that it is an estimate, and our assumptions will be monitored by the DMC throughout the study. They will advise whether a sample size adjustment is necessary.

7.2.3 Assessment of efficacy

Primary outcome: The evaluation of the primary outcome will be performed using a negative binomial model that includes the minimisation factors (stroke service, living alone or with others, aged >65 years or <=65 years and baseline modified Barthel Index (MBI) score of >14 or <=14). The model will incorporate exposure time to estimate the between group difference which will be summarised using the incident rate ratio (IRR) and its associated 95% confidence interval.

The primary analysis will be 'as randomised' with no imputation of missing data.

Sensitivity analyses: Sensitivity analyses will be conducted to investigate the impact of missing data using techniques such as multiple imputation and may also include alternative models where visual inspection of the baseline variables show marked imbalances in potentially prognostic variables, between groups. Further sensitivity analyses may be performed if participants show major non-compliances (e.g., who do not receive the intervention when randomised to do so or receive the intervention when randomised to standard care alone).

Sub-group analyses: Exploratory subgroup analyses for the primary outcome will be performed according to the minimisation variables by including appropriate interaction terms

Page 39 of 53

FISS Protocol Final Version 1.0 date 24-Jul-2025

in the primary model. The interpretation of any subgroup effect will be based on the interaction tests (i.e., evidence of differential treatment effects in different subgroups). It is acknowledged that these investigations will not be adequately powered.

Secondary outcomes: Secondary outcomes will be analysed using appropriate regression models which include the minimisation factors and the baseline value of that variable where available. Continuous outcomes will be analysed using linear mixed models and count/rate outcomes will be analysed using negative binomial models. Associated measures of the between treatment difference, such as the difference in means or incidence rate ratio, will be presented alongside 95% confidence intervals. The secondary analyses will be considered supportive to the primary and interpreted in that light, and no multiplicity adjustments will be made.

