6.1.1 Baseline

Following consent but prior to randomisation, baseline data will be collected, this will include (but not limited to) demographic and contact details and the following baseline questionnaires:

- Nottingham Extended Activities of Daily Living (NEADL) [14]
- Short Falls Efficacy Scale-International (Short FES-I) [13]
- Patient Health Questionnaire 8 (Participant PHQ-8) [15]
- Modified Barthel Index (MBI)
- Quality of Life (EQ-5D-5L) [16]
- Health Resource Questionnaire
- Patient Health Questionnaire 8 (Carer PHQ-8)*

Baseline data will be collected by research staff or FISS trained stroke healthcare professionals once they are discharged, either in person at the participant's home or over the phone, where possible. Data will be captured directly into REDCap, or where an electronic device is not available, into a paper workbook transcribed into REDCap.

Participants will be randomised using a web-based, concealed randomisation system to receive either the SAF intervention in addition to usual care or usual care alone. The participant

Page 33 of 53

FISS Protocol Final Version 1.0 date 24-Jul-2025

will be told by a member of stroke service which arm of the study they have been randomised to at the time of randomisation (where possible) or as soon after randomisation is completed.

Baseline data collection and randomisation is likely to take place on the same day and will need to be collected within 28 days of discharge as per remote consent. Where this is not possible, randomisation can take place remotely and the participant contacted to inform them of their treatment allocation. This will need to be within 1 or 2 days of collecting the baseline data.

*The Carer PHQ will be posted to the participant's contact address once the participant is randomised. The baseline carer PHQ will be completed by the carer (electronic or post) and returned to the NCTU. Where randomisation is done in person and the carer is available, this can be done at the point of randomisation.

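### The primary model enters age and baseline MBI only as two-level splits, giving up a modest amount of precision that the collected data could supply

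*Protocol*

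**What the plan says.** Section 7.2.3 of the protocol does not leave the covariate form open. Besides stroke service and living alone or with others, the primary negative binomial model includes participants "aged >65 years or <=65 years and baseline modified Barthel Index (MBI) score of >14 or <=14". These are the minimisation categories of Table 4 (section 5.2.1), where age and MBI are each described as related to the chance and the severity of falling.

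The full values exist. Section 6.1.1 has the MBI completed after consent and before randomisation, along with NEADL, Short FES-I, PHQ-8 and EQ-5D-5L. Section 12.3 records date of birth.

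Further covariates appear only under sensitivity analyses. Section 7.2.1 says that these "may also include further co-variates if visual inspection of baseline variables show marked imbalanced between groups". Section 7.2.3 repeats the idea as an optional alternative model and limits it to potentially prognostic variables. Sections 7.2.3 and 7.2.5 rule out imputation in the primary analysis.

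**The concern.** A two-level split treats everyone on one side of the cut as equal. If fall risk changes gradually with age and MBI, part of their predictive information stays in the residual overdispersion and widens the confidence interval for the incidence rate ratio.

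This matters more here than in many trials because overdispersion dominates the variance behind the sample size: 2.2 of 3.197 units, or 69%. Explaining differences between people is the only way to reduce that part without recruiting more of them. With a log link and no treatment-by-covariate interaction, the rate ratio keeps its meaning after adjustment, so the gain does not change the target of estimation.

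**Working it through.** **Inputs (protocol section 7.2.2).** Control rate: "assuming an annual falls rate of 2.5 falls per year per participant". Rate ratio 0.67, giving 1.675 falls per year. Overdispersion k: "upper limit of the 95% confidence interval for the overdispersion parameter (FinCH study; 1.1"). Power 90%, two-sided 5%, follow-up one year, 1:1 allocation.

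**Step 1: reproduce the plan's figure.** Section 7.2.2 says "416 evaluable participants would be required to detect" the 33% reduction. The formula is

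n per arm = (1.960·√V0 + 1.282·√V1)² / ln(0.67)²

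- V1 = 1/2.5 + 1/1.675 + 2 × 1.1 = 3.197.
- V0 at the pooled rate 2.0875 = 2/2.0875 + 2.2 = 3.158.
- n = (3.483 + 2.291)² / 0.1604 = 207.9, so 208 per arm and 416 in total, an exact match.
- 208/0.9 gives 232 per arm, or 464 randomised.

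Using V1 in place of V0 gives 210 per arm. No covariate enters the calculation. With the V1 formula, power at 208 per arm is 89.8%.

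**Step 2: what a split keeps.** For a normally distributed score cut so that a proportion p lies on one side, the split retains φ(c)²/[p(1−p)] of the explained variance, where c is the normal quantile of p. This is 0.637 at 50/50 and 0.539 at 75/25. The actual proportions are not in the protocol, so both are shown.

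**Step 3: carry this into the variance.** Let r be the share of k = 1.1 that full-scale age and MBI explain. The protocol gives no value, so r is an assumption, shown from 5% to 40%.

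- Full scale: k = 1.1(1 − r).
- 50/50 split: k = 1.1(1 − 0.637r).

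Example at r = 20%: full-scale k = 0.880, variance 0.997 + 1.760 = 2.757. Split k = 0.960, variance 0.997 + 1.920 = 2.917. Ratio 2.917/2.757 = 1.058.

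| r | Power at 208 per arm, split vs full (50/50) | Variance ratio, 50/50 | Variance ratio, 75/25 | n per arm for 90% power, split vs full (50/50) |
|---|---|---|---|---|
| 5% | 90.4% vs 90.8% | 1.013 | 1.016 | 205 vs 203 |
| 10% | 91.0% vs 91.7% | 1.027 | 1.034 | 201 vs 196 |
| 20% | 92.2% vs 93.6% | 1.058 | 1.074 | 192 vs 181 |
| 30% | 93.4% vs 95.2% | 1.095 | 1.120 | 182 vs 167 |
| 40% | 94.5% vs 96.7% | 1.138 | 1.175 | 173 vs 152 |

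The last column uses the V1 formula, so its unadjusted counterpart is 210. With 75/25 splits at r = 40%, power is 93.8% against 96.7%, a gap of 2.9 points.

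**Step 4: check by simulation.** In 400 simulated trials per setting (416 participants, two covariates, 50/50 splits), the mean model standard errors of the log rate ratio, split vs continuous, were:

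- r = 10%: 0.1185 vs 0.1169
- r = 20%: 0.1139 vs 0.1107
- r = 30%: 0.1103 vs 0.1055
- r = 40%: 0.1065 vs 0.1000

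Squaring the ratios gives 1.028, 1.059, 1.093 and 1.134, in line with the 50/50 column. The standard errors themselves are lower than the formula's, because the simulation's residual overdispersion falls further (0.458 against 0.66 at r = 40%). The relative cost of splitting is the same.

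**The case against.** The strongest reply is that nothing promised is lost. Adjusting for the factors in the form used for minimisation is a standard, valid analysis. The sample size assumed no covariate gain, so the split factors can only improve on it: 90.4% to 94.5% power in the table. The size of any further gain rests on an assumed r, on roughly normal scores and on a smooth relation with the log rate; if risk really stepped at 65 years and at an MBI of 14, splitting would cost nothing. The k of 1.1 is also a deliberately cautious upper limit, which enlarges the share of variance open to explanation. All of this stands, and it limits the point to an efficiency improvement.

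Four stronger readings are tempting and not supported:

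- **That the primary model chooses covariates by visual inspection.** Sections 7.2.1 and 7.2.3 both place this under optional sensitivity analyses. The primary covariates are fixed.
- **That the trial is underpowered or its estimate biased.** The 416/464 reproduces, and the split-adjusted estimate is valid.
- **That the saving is large.** A simulation giving age and MBI log-rate standard deviations of 0.45 each yields a variance ratio of 1.16, or about 67 of 416 participants. Its continuous-model standard error of 0.0973 implies a residual k of (0.0973² × 208 − 0.997)/2 ≈ 0.49, so two variables would have to remove about 56% of the overdispersion.
- **That Short FES-I and NEADL belong in the primary model.** Their value depends on what they predict beyond age and MBI, which is unknown and was not calculated. Nor does the protocol make their completion a condition of randomisation, so missing scores would collide with the no-imputation rule.

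The lack of a baseline falls count in the model is no fault either, since section 6.1.1 and Table 6 list none.

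**Conclusion.** The point holds as a modest improvement available at almost no cost. Section 7.2.3 fixes two-level terms for two variables that the protocol itself regards as prognostic and holds in full. If those variables explain 5% to 40% of an overdispersion of 1.1, the cost in variance is about 1% to 14% with 50/50 splits and up to about 18% with 75/25 splits, equivalent to about 0.4 to 2.9 points of power. The assumed r drives the answer and cannot be narrowed from the protocol.

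The visual-inspection trigger is a lesser, separate weakness. It names no variables and no threshold, and it needs data by arm, which section 5.2.2 withholds from the study statistician until the SAP is approved and the database locked. The choice would therefore be made with the allocation known. It affects sensitivity analyses only.

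**What to change.** In section 7.2.3, and in the SAP, before allocation is released:

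1. Keep stroke service and residence as factors in the primary model. Enter age in years at randomisation and baseline MBI score as continuous terms, with one functional form stated in advance. Linear terms use no more parameters than the splits.
2. Keep the 65-year and 14-point cut-points for minimisation and for the subgroup analyses.
3. Run the currently planned factor-only model as a sensitivity analysis.
4. Optional, in sensitivity analyses only: replace the visual-inspection wording in sections 7.2.1 and 7.2.3 with a named list of prognostic baseline covariates, for example Short FES-I and NEADL, and state how missing baseline scores are handled.

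The cost is protocol and SAP wording: no extra participants, visits or questionnaires. Age and MBI should be complete because minimisation needs both, so items 1 to 3 do not touch the no-imputation rule. Only item 4 needs a missing-data rule.
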